9.2 OVERVIEW OF STUDY DESIGN

This single-arm trial will have 1 planned interim analysis and a final analysis.

The primary endpoint is whether a patient achieves an overall response (defined as a complete response (CR) or partial response (PR)). The trial is designed to test the null hypothesis that standard therapy has an overall response (CR+PR) rate of 10% versus the alternate hypothesis that ECP plus standard therapy has a CR+PR rate not equal to 10% (the expected rate $\geq 27\%$). After the first 50% (24/48) of the patients have been treated for at least 4 weeks (or fewer if patients discontinued treatment), significance will be declared if the CR+PR 2-sided *P* value versus the stated alternative is < 0.005 , corresponding to an observed CR+PR rate $> 48\%$. Based on the primary endpoint analysis and review of the safety results available at the time of the interim analysis, consideration will be given, in the absence of safety concerns, to continue or stop the study for success or futility. Enrollment will not be placed on hold during the interim analysis. A final analysis will be performed after all 48 patients have been treated for at least 4 weeks. In this final analysis, significance will be declared if the CR+PR 2-sided *P* value versus the stated null is < 0.049 . The overall Type I error rate and power for this design are 5% and 90.4%, respectively.

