	
rate of 10% versus the alternate hypothesis that ECP plus standard therapy has a CR+PR rate not equal to 10% (the expected rate $\geq 27\%$). The overall Type I error rate and power for this design are 5% and 90.4%, respectively.
 
This single-arm trial will have 1 interim analysis and a final analysis. After the first 24 patients enrolled into the study have completed at least 4 weeks of ECP treatment, significance will be declared if the CR+PR 2-sided P value vs the stated alternative is < 0.005, corresponding to an observed CR+PR rate $> 48\%$. A final analysis will be performed after all 48 patients enrolled into the study have been treated for at least 4 weeks. In this final analysis, significance will be declared if the CR+PR 2-sided P value vs the stated null is < 0.049.

Statistical methods	
All baseline demographic and disease characteristics will be summarized. The primary endpoint of overall response (CR+PR) at Day 28 (Week 4) will be summarized by frequency tabulation and analyzed using exact Binomial test and confidence interval. Secondary endpoints of response at Week 8 (Day 56) and Week 12 (Day 84) will be analyzed in the same manner. Other endpoint data collected in the Treatment and Follow-up Period will be summarized appropriately.
 
All AE data will be fully listed by investigator terms and Medical Dictionary for Regulatory Activities (MedDRA) preferred term. Adverse event data will be summarized by system organ classification and preferred term. Vital signs and laboratory values will be summarized by visit and numbers of patients, with excursions outside the normal reference range summarized.
 
Patients who voluntarily cease to receive treatment early will not be replaced. Patients may be replaced if they are enrolled in the trial but are not treated. If a patient has received any ECP treatments and is administered a second-line therapy other than ECP, or discontinues study treatment, that patient will be considered a nonresponder and may not be replaced.

TABLE OF CONTENTS

SIGNATURE PAGE.....	3
SIGNATURE PAGE.....	4
PROTOCOL SYNOPSIS	5
TABLES IN TEXT	14
FIGURES IN TEXT.....	14
LIST OF ABBREVIATIONS AND DEFINITIONS OF TERMS.....	15
1. INTRODUCTION	17
1.1 Background.....	17
2. STUDY OBJECTIVES	21
2.1 Primary Objective	21
2.2 Secondary Objectives.....	21
3. OVERALL DESIGN AND PLAN OF THE STUDY	22
3.1 Overview	23
3.2 Endpoints.....	23
3.2.1 Primary Endpoint.....	23

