9.3.1 Analysis of Primary Endpoint

The primary endpoint is the proportion of patients who achieve an overall response (CR+PR) after 4 weeks (Day 28), or fewer treatments if they discontinued treatment, of ECP treatment. Patients must receive at least one treatment. Patients will be evaluated by the treating physician for the presence or absence of aGvHD manifestations of the skin, liver, and gut; source data will be collected for each patient and entered into the eCRF, and a scoring algorithm will be applied to calculate the grade of aGvHD using the modified IBMTR Severity Index. If a Patient is administered a second-line therapy other than ECP for the treatment of aGvHD, or discontinues study treatment, that Patient will be considered a nonresponder. The primary endpoint will be summarized by frequency tabulation and analyzed using exact Binomial test and confidence interval. The formal statistical analysis and evaluation of response is based on at least 4-weeks ECP treatment data only.

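### The interim success rule equates P < 0.005 with an observed response rate above 48%, but against the 10% null P < 0.005 is reached at 8/24 (33.3%), so 8 to 11 responders of 24 give opposite decisions

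*Combined protocol and SAP*

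**What the plan says.** Section 9.2 tests the "null hypothesis that standard therapy has an overall response (CR+PR) rate of 10" percent against a "CR+PR rate not equal to 10% (the expected rate $\geq 27" percent). The interim analysis comes "After the first 50% (24/48) of the patients have been treated for at least 4 weeks". At that point "significance will be declared if the CR+PR 2-sided" P "value versus the stated alternative is < 0.005 , corresponding to an observed CR+PR rate $> 48" percent. The synopsis (Power and sample size) gives the same rule: "value vs the stated alternative is < 0.005, corresponding to an observed CR+PR rate" above 48%.

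For the final analysis of 48 patients, section 9.2 uses 2-sided P < 0.049, this time measured against the stated null. Section 9.3.1 says that the primary endpoint is "analyzed using exact Binomial test and confidence interval". It also counts treated patients who discontinue as nonresponders, so the interim denominator stays at 24.

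**The concern.** The rule gives a P threshold and a response-rate threshold and presents them as the same boundary. A rate of 48% among 24 patients is nearly five times the null rate, so its exact P should lie far below 0.005. If the two thresholds fall at different responder counts, some interim results are significant under one half of the sentence and not under the other.

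The reference for the P value is also unclear: the interim sentence measures it against the alternative, the final sentence against the null.

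This is the only interim efficacy boundary in the protocol. It feeds a decision on continuing or stopping for success or futility, in an open-label, single-arm trial that section 3.4 links to a possible application for accelerated approval. Choosing between the two halves once the count is known would be a data-driven decision.

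**Working it through.** **Inputs.** Null rate 10%, expected rate 27%, interim n = 24, 2-sided P < 0.005, rate above 48% (section 9.2); exact binomial test (section 9.3.1). The protocol does not say how the exact P is made two-sided, so both usual conventions are shown.

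**Step 1: the rate threshold as a count.** 11/24 = 45.8% fails and 12/24 = 50.0% passes. A rate above 48% therefore means at least 12 of 24.

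**Step 2: the P threshold as a count, against 10%.** With X ~ Binomial(24, 0.10), the upper tail is P(X ≥ x). The doubled P is twice that tail. The minimum-likelihood P sums the probabilities of all outcomes no more likely than x; for the counts below it equals the upper tail.

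| Responders | Rate | Doubled P | Minimum-likelihood P | P < 0.005? | Rate > 48%? |
|---|---|---|---|---|---|
| 7 | 29.2% | 0.0149 | 0.0075 | no | no |
| 8 | 33.3% | 0.0034 | 0.0017 | yes | no |
| 9 | 37.5% | 0.00064 | 0.00032 | yes | no |
| 10 | 41.7% | 0.00010 | 0.00005 | yes | no |
| 11 | 45.8% | 0.000014 | 0.000007 | yes | no |
| 12 | 50.0% | 0.0000017 | 0.0000008 | yes | yes |

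Both conventions put the P boundary at 8/24. The two thresholds are four responders apart. At the first count that passes the rate rule, the doubled P is about 3,000 times smaller than 0.005 (0.005 / 0.0000017).

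**Step 3: can the stated 48% be reproduced another way?**

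- Exact test against 27%: 12/24 gives P = 0.027 (doubled) or 0.019 (minimum likelihood), and 13/24 gives 0.0088 or 0.0049. The boundary is 14/24 (58.3%, doubled P = 0.0024) or 13/24 (54.2%).
- Normal approximation, p + 2.807 × √(p(1 − p)/24): 0.10 + 2.807 × 0.0612 = 27.2% against 10%, and 0.27 + 2.807 × 0.0906 = 52.4% against 27%.
- Wald test against 10%: first met at 10/24 (41.7%).
- Exact test against 10% at n = 19, the first interim size named in section 3.4: 7/19 (36.8%).

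None of these has 12/24 as its first significant count. The nearest match is a normal approximation against 27% at one-sided 0.01: 0.27 + 2.326 × 0.0906 = 48.1%. That is not the 2-sided 0.005 in the protocol.

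**Step 4: how often the two rules disagree (10% reading).**

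| True rate | P(8 to 11 of 24) | P(≥ 8 of 24) | P(≥ 12 of 24) |
|---|---|---|---|
| 27% | 29.6% | 31.0% | 1.4% |
| 30% | 40.4% | 43.5% | 3.1% |
| 40% | 59.5% | 80.8% | 21.3% |
| 50% | 38.7% | 96.8% | 58.1% |

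**Step 5: effect on the whole design.** The final rule P < 0.049 is first met at 10/48 (doubled P = 0.037; 9/48 gives 0.093 doubled or 0.053 by minimum likelihood). The exact two-stage calculation with that final cut gives:

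- interim boundary 8/24: upper-tail error 1.92% at a true 10%, power 87.2% at 27%;
- interim boundary 12/24: 1.87% and 87.2%.

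**The case against.** **Error rates barely move.** Step 5 shows that type I error and power are almost the same under either boundary. A trial with 8 to 11 responders at the interim goes on to final success with probability 99.7% at a true 27%, and above 99.99% at 40%. The conflict affects when success is declared far more than whether it is. Enrollment also continues during the interim analysis, and stopping is only to be considered. All of this stands. It limits the harm, but the declaration of significance itself is not worded as discretionary.

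**The 8-to-11 range assumes a test against 10%.** If the wording about the alternative meant a test against 27%, counts of 8 to 11 would fail both rules. The conflict would shrink to 12/24, or to 12 and 13 of 24, with probability 0.9% to 1.2% at a true 27%. The range is indeed conditional on the 10% reading. But the stated alternative is that the rate differs from 10%, so 10% is the natural reference, and the 27% reading does not yield 48% either.

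**The true rate may be higher.** The introduction cites overall response of 66% and 76%, and improvement in 70%, in other ECP series. At 66%, 70% and 76% the chance of 8 to 11 of 24 is 3.3%, 1.1% and 0.1%. These studies are retrospective or small, and the design itself is planned on 27%.

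**Other documents may settle it.** Section 9.3 refers to a formal analysis plan and section 8.2 to a DSMB charter. Either could state a count, but the text provided does not, and the protocol sentence would still contradict itself.

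**Conclusion.** The concern holds. Under the named test and the 10% null, P < 0.005 corresponds to at least 8/24 (33.3%), not to a rate above 48%. The two criteria give opposite declarations at 8, 9, 10 and 11 of 24. The chance of such a result is 29.6% at the planned 27%, rises to 59.5% at 40%, and is small if the true rate is 66% or more.

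The conclusion assumes 24 evaluable patients and an exact test against 10%. It does not depend on the two-sided convention. Under the alternative reading of a test against 27%, the conflicting counts change but the mismatch remains.

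This is not a threat to type I error or power. It is a prespecified decision threshold that is wrong as written, and it must be corrected before the interim analysis.

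**What to change.** State the boundary once, as a responder count, in both section 9.2 and the synopsis:

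- If P < 0.005 is intended: at least 8 of 24 responders (33.3% or more), exact 2-sided P against the 10% null below 0.005. Delete the 48% figure and replace the reference to the alternative with one to the null.
- If a hurdle near 50% is intended: at least 12 of 24 responders. Delete the interim P threshold together with its reference to the alternative.

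Name the two-sided convention for the exact test. Section 3.4 still describes two interim analyses at N = 19 and N = 38; bring it into line with the single 24-patient interim, so that the boundary belongs to an analysis that all sections describe alike.

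The cost is a wording amendment to the protocol, carried into the analysis plan. No extra patients or data are needed. It has to be done before anyone sees the interim results.

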9. STATISTICAL METHODS

9.1 PLANNED SAMPLE SIZE

A total of 48 patients with steroid-refractory grade B-D aGvHD will be enrolled and receive at least one ECP treatment. The trial is designed to test the null hypothesis that standard therapy has an overall response (CR+PR) rate of 10% versus the alternate hypothesis that ECP plus standard therapy has a CR+PR rate not equal to 10% (the expected rate $\geq 27\%$). The overall Type I error rate and power for this design are 5% and 90.4%, respectively.

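### The stated 5% Type I error and 90.4% power are not those of the planned exact test, which attains about 2.5% and 87%

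*Combined protocol and SAP*

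**What the plan says.** Section 9.1 fixes the sample size ("A total of 48 patients with steroid-refractory grade B-D aGvHD will be enrolled and receive at least one ECP treatment") and sets the "null hypothesis that standard therapy has an overall response (CR+PR) rate of 10" percent, with an expected rate of at least 27% on ECP. It then states: "The overall Type I error rate and power for this design are 5% and 90.4%, respectively". Section 9.2 repeats that sentence, and the synopsis carries the same figures.

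On the looks, Section 9.2 says: "This single-arm trial will have 1 planned interim analysis and a final analysis". The interim comes "After the first 50% (24/48) of the patients have been treated for at least 4 weeks". Success is declared there if the two-sided P "value versus the stated alternative is < 0.005 , corresponding to an observed CR+PR rate" above 48%. At the end, success is declared if the two-sided P "value versus the stated null is < 0.049".

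Section 9.3.1 and the synopsis specify an exact binomial test for the primary endpoint. No boundary family or spending function is named, and neither the 5% nor the 90.4% is derived.

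**The concern.** Section 3.4 says a single-arm trial of this kind could support an application for accelerated approval. Its error rate, power and critical values are then design properties that a regulator will recompute. With 48 patients and a null rate of 10%, an exact test can attain only a few error levels, so a nominal 5% can lie well away from the level actually attained. Power moves with it. The question is whether 5% and 90.4% describe the test that will be run or some approximation to it.

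**Working it through.** **Inputs.** Null rate 10%, expected rate 27%, n = 48 (Section 9.1); interim at 24, two-sided levels 0.005 and 0.049 (Section 9.2); exact binomial test (Section 9.3.1). Futility is mentioned in Section 9.2 without a boundary, so it is treated as non-binding.

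**Step 1: the stated figures by normal theory.** The two-sided critical values are z = 2.807 (0.005) and z = 1.969 (0.049). The correlation between looks is √(24/48) = 0.707. Total error = 1 − P(|Z1| < 2.807 and |Z2| < 1.969) = 5.09%. Power at 27% for the final look alone is Φ[(0.17·√48 − 1.969·√0.09) / √(0.27·0.73)] = Φ[(1.178 − 0.591)/0.444] = Φ(1.32) = 90.7%; with both looks it is 91.1%. These lie close to 5% and 90.4% without matching the power exactly. The stated figures may therefore come from a normal approximation, but the plan does not say so.

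**Step 2: exact cut-offs against 10%.** The two-sided exact P value sums the probabilities of all outcomes no more likely than the one observed.

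| Result | Exact two-sided P | Level | Rejects? |
|---|---|---|---|
| 7/24 | 0.0075 | 0.005 | no |
| 8/24 | 0.0017 | 0.005 | yes |
| 9/48 | 0.0527 | 0.049 | no |
| 10/48 | 0.0251 | 0.049 | yes |
| 0/48 | 0.0132 | 0.049 | yes (lower tail) |

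Doubling the smaller tail instead gives the same cut-offs.

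**Step 3: attained error and power.** With X1 and X2 the responders in the first and second 24 patients and c the interim cut-off:

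P(reject) = P(X1 ≥ c) + Σ over x < c of P(X1 = x)·P(X2 ≥ 10 − x) + P(0/48).

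| | c = 8 (P < 0.005 against 10%) | c = 12 (observed rate > 48%) |
|---|---|---|
| Error, interim | 0.17% | < 0.001% |
| Error, final upper tail | 1.75% | 1.87% |
| Error, final lower tail | 0.64% | 0.64% |
| **Total error, two-sided** | **2.55%** | **2.51%** |
| Efficacy direction only | 1.92% | 1.87% |
| Chance of crossing at the interim, true rate 27% | 31.0% | 1.4% |
| **Power at 27%** | **87.2%** | **87.2%** |

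**Step 4: the two interim statements.** An observed rate above 48% needs at least 12 of 24 (11/24 = 45.8%). Against 10%, P falls below 0.005 already at 8/24 (33.3%). Read literally as a test against 27%, the P value at 12/24 is 0.019, so that reading does not give 48% either.

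**Step 5: other tests.** At the same levels, a score test gives 5.45% error, a continuity-corrected test 2.55%, a Wald test 17.0%, and one-sided exact P values 4.64%. None gives 5% with 90.4% power.

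**The case against.** The best defence is that 5% is a ceiling and a discrete exact test always sits below its nominal level. That stands as far as error control goes: 2.55% is conservative, and no false-positive protection is lost. It does not rescue the wording. The plan gives 5% as the overall error rate of the design, beside a power quoted to one decimal that the exact test misses by 90.4 − 87.2 = 3.2 points.

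A reader might infer something stronger, that the pair 0.005/0.049 inflates the error above 5%. By normal theory it totals 5.09%; 0.005/0.048 gives 4.99% and 0.003/0.049 gives 5.00%, so the stated pair looks like a mixture of two boundaries. Rounding of the two levels does not bring it to 5% (range 5.02% to 5.16%). But the excess rounds to the stated whole percent and belongs to a test the plan does not use. If the 48% threshold governs the interim, even the normal-theory total is only 4.90%. No result would be judged differently at 0.048.

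A reader might also infer that the interim rule is simply 8/24. Section 9.2 does not support this, because it also ties interim success to a rate above 48%. Writing in 8/24 without comment would raise the chance of crossing at the interim from 1.4% to 31% at a true rate of 27%.

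**Conclusion.** The point holds, and it is minor. The stated 5% and 90.4% are not the operating characteristics of the planned exact test, which attains 2.5% to 2.6% two-sided error (1.9% for efficacy) and about 87% power at 27%, whichever interim statement governs. Type I error is controlled, and the documents give no ground for calling the trial inflated.

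This rests on four assumptions: the exact test applies at both looks; the tests are against 10%, apart from the alternative 48% interim rule; futility is non-binding; and the single-interim design of Section 9.2 governs. Section 3.4 still describes two interim looks, at 19 and 38 patients, but gives no levels for them, so that version cannot be checked.

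**What to change.** 1. Reconcile the interim wording in Section 9.2 and the synopsis. The 0.005 level, the reference to the alternative, and the rate above 48% cannot all describe one test against 10%. The sponsor must say which rule was intended.
2. State the interim and final rules as responder counts under the exact test, and say which two-sided exact P value is used. The final rule is 10 or more of 48, with 0 of 48 in the lower tail.
3. In Sections 9.1 and 9.2 and the synopsis, replace 5% and 90.4% with the attained values: about 2.5% to 2.6% two-sided (1.9% for efficacy) and about 87% power at 27%.
4. Optionally, change 0.049 to 0.048 and name the boundary family. The final cut-off stays at 10/48. Lowering the interim level to 0.003 instead is less neutral: with doubled tails, P at 8/24 is 0.0034 and would no longer qualify.

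Items 2 to 4 cost a few sentences and leave the sample size as it is. Item 1 is a real decision, because it settles when early success may be declared, and it should come first.

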9.3 EFFICACY ANALYSES

A formal statistical analysis plan will be developed prior to first patient entered that will provide full details of analysis methods and analysis populations.

9.3.1 Analysis of Primary Endpoint

The primary endpoint is the proportion of patients who achieve an overall response (CR+PR) after 4 weeks (Day 28), or fewer treatments if they discontinued treatment, of ECP treatment. Patients must receive at least one treatment. Patients will be evaluated by the treating physician for the presence or absence of aGvHD manifestations of the skin, liver, and gut; source data will be collected for each patient and entered into the eCRF, and a scoring algorithm will be applied to calculate the grade of aGvHD using the modified IBMTR Severity Index. If a Patient is administered a second-line therapy other than ECP for the treatment of aGvHD, or discontinues study treatment, that Patient will be considered a nonresponder. The primary endpoint will be summarized by frequency tabulation and analyzed using exact Binomial test and confidence interval. The formal statistical analysis and evaluation of response is based on at least 4-weeks ECP treatment data only.

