6.2.1 Selection of Timing and ECP Treatment in the Study

The selection and timing of ECP treatments is based on the Principal Investigator's assessment of patient status such that ECP will be administered 3 times per week every week for 4 weeks (Weeks 1-4), followed by 2 times per week every week for 8 weeks (Weeks 5-12).

Patients must be enrolled and receive their first ECP treatment within 1 week (7 days) after being diagnosed as having steroid-refractory aGvHD. Patients are expected to receive the stated number of treatments per treatment week (7 days) \pm 2 days, and a total of no more than 12 ECP treatments for the first 28 days. A maximum of 28 and a minimum of 1 ECP treatments will be given per patient during the 12-week treatment period.

Week 1 (7 days) begins when the first ECP treatment is received (Day 1 of Week 1). Extracorporeal photopheresis treatments given within \pm 2 days of the expected treatment week will not be considered a protocol deviation.

After completion of the 12-week Treatment Period, patients may continue ECP treatment on commercial product at the discretion of the Principal Investigator.

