6.6.1 Early Cessation of Study Treatment

Patients *may* voluntarily stop receiving therapy at any time. The patient's legal guardian/legally authorized representative may choose to stop a patient's therapy at any time.

If a patient voluntarily ceases to receive therapy, the primary reason must be requested and, if provided, will be recorded on the Study Termination page of the eCRF.

The Principal Investigator and/or the Sponsor may also judge that early cessation of treatment is warranted for any one of the following reasons:

- Occurrence of AEs that pose a risk to safe participation.

- Abnormal laboratory value(s) that pose a risk to safe participation.
- Abnormal test procedure result(s) that pose a risk to safe participation.
- Unsatisfactory therapeutic effect.
- Condition no longer requires treatment.
- Significant protocol deviation.
- Patient non-compliance with protocol requirements.

Unless a patient/legal guardian/legally authorized representative withdraws study consent, patients will continue to be followed as per the trial protocol and clinical assessment schedule to ensure that full, intent-to-treat follow-up data are obtained.

For patients who are lost to follow-up, the Principal Investigator should show due diligence by documenting in the source documents steps taken to contact the patient (e.g., dates of telephone calls, emails).

Patients who voluntarily cease to receive treatment early will not be replaced. Patients will be replaced if they are enrolled in the trial but are not treated.

If a patient has received any ECP treatments and is administered a second-line therapy other than ECP for the treatment of aGvHD, or discontinues study treatment, that patient will be considered a nonresponder and may not be replaced.

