7. STUDY CONDUCT

7.1 SCHEDULE OF ASSESSMENTS

Table 1. Schedule of Assessments

Assessments and Procedures	Screening	Treatment Period, weeks (+/- 2 days)												Follow-Up Period, weeks		Early Study Termination
		1	2	3	4 (Day 28) Primary Endpoint	5	6	7	8 (Day 56) Secondary Endpoint	9	10	11	12 (Day 84) Secondary Endpoint	16	26	
Informed consent/assent form	X															
Inclusion/exclusion criteria	X															
Focused medical history	X															
Transplant history	X															
Corticosteroid dosing	X	X	X	X	X	X	X	X	X	X	X	X	X	X		X
Complete physical examination	X				X				X				X	X		X
Targeted physical examination		X	X	X		X	X	X		X	X	X				
Urine Pregnancy test ^a	X	X	X	X	X	X	X	X	X	X	X	X	X			X
Vital signs	X	X	X	X	X	X	X	X	X	X	X	X	X	X		X
Lansky Performance Status	X				X				X				X	X		X
Local laboratory analyses ^b	X	X	X	X	X	X	X	X	X	X ^h	X	X	X	X		X
Assess aGvHD status ^c	X	X	X	X	X	X	X	X	X	X	X	X	X ⁱ	X		X
Baseline total bilirubin level and aGvHD assessment ^d		X														
Total bilirubin level and primary endpoint aGvHD status assessment ^e					X											
Total bilirubin level and secondary endpoint aGvHD status assessment ^f									X				X			
Number of ECP treatments ^g		3	3	3	3	2	2	2	2	2	2	2	2			

Concomitant medications	X	X	X	X	X	X	X	X	X	X	X	X	X	X	X	X
Adverse events	X	X	X	X	X	X	X	X	X	X	X	X	X	X	X	X
Nonrelapse mortality		X	X	X	X	X	X	X	X	X	X	X	X	X	X	X
Survival		X	X	X	X	X	X	X	X	X	X	X	X	X	X	X
Early study termination ^j																X

^a If the result of the urine test is positive, blood must be drawn for a serum human chorionic gonadotropin (HCG) level and analyzed locally. A serum test may be performed in place of the urine test.

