^b At a minimum, a bilirubin level should be checked before the first ECP treatment of each week to assist in assessing aGvHD status of the previous week. Platelets and total WBC count should be checked before each scheduled ECP treatment as clinically indicated to ensure that they meet pre-ECP safety parameters. Hematocrit should be checked according to the CELLEX System Operator’s Manual. Ionized calcium may be checked, at the discretion of the Principal Investigator. A new calculation of Total Blood Volume is necessary before each treatment to estimate the safe extracorporeal blood volume that may be allowed for the patient undergoing treatment. These calculations should be performed using the current weight (recorded at the first visit of the week) and current hematocrit (drawn after the last photopheresis treatment and within 48 hours before the next photopheresis treatment).

^c After the baseline aGvHD assessment at the beginning of Week 1, aGvHD assessments should be performed within the weekly treatment window (± 2 days) after the last ECP treatment of each treatment week.

^d A baseline aGvHD assessment, including blood sampling for total bilirubin should be performed before the first ECP treatment of Week 1.

^e The assessment of aGvHD for the primary endpoint must occur at Day 28 (± 2 days) and must include a total bilirubin level.

^f The assessment of aGvHD for the secondary endpoint must occur at Days 56 and 84 (± 2 days) and must include a total bilirubin level.

^g Patients should be told emphatically to wear UVA-absorbing, wrap-around sunglasses and to cover exposed skin or use a sunblock (SPF 15 or higher) for the 24 hour period following treatment with methoxsalen, whether exposed to direct or indirect sunlight in the open or through a glass window.

^h These laboratory assessments should be performed monthly, before the first ECP treatment of the week at Weeks 5 and 9:

- CBC with differential (WBC, platelets, hemoglobin, hematocrit, neutrophils, lymphocytes, basophils, eosinophils, and monocytes); absolute neutrophil count.
- Electrolyte panel (sodium, potassium, chloride, bicarbonate, BUN, creatinine, and glucose), BUN/creatinine ratio, calcium, phosphorous, and magnesium.
- AST, ALT, GGT, total bilirubin, direct bilirubin, indirect bilirubin, alkaline phosphatase, and lactate dehydrogenase.

ⁱ The assessment of aGvHD must be +/- 2 days of the endpoint assessments

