Patients should be explicitly instructed to wear UVA-absorbing, wrap-around sunglasses and cover exposed skin or use a sunblock (SPF 15 or higher) for the 24 hour period following treatment with methoxsalen, whether exposed to direct sunlight or indirect sunlight through a glass window.

Primary and Secondary aGvHD Endpoint Assessments (Weeks 4, 8, and 12)

Assessments of aGvHD status (including total bilirubin, corticosteroid dosing, Lansky Performance Status, etc.) for the purpose of the primary and secondary endpoint analyses should be performed at Days 28 (± 2), 56 (± 2) and 84 (± 2), respectively.

Concomitant Medications

All concomitant medications taken by patients during the Treatment Period, including those medications taken between visits, will be recorded on the Prior and Concomitant Medication Report Form of the eCRF. Concomitant medications should be recorded on a weekly basis.

Adverse Events

Patients will be asked about AEs that may have occurred after the patient signed and dated the ICF. Each patient will be asked about AEs using the non-specific question, "How have you been since your last visit?" Any AEs elicited by this question will be recorded on the Adverse Event Report Form of the eCRF, as well as any AEs spontaneously volunteered by the patient or observed by the study staff.

Nonrelapse Mortality

Nonrelapse mortality is defined as death due to any cause, with death due to relapse as a competing risk [Das-Gupta et al., 2014b].

Survival

Recipient Death Information must be entered into the eCRF within 24 hours of knowledge of a patient's death. Once the cause of death is determined, the information must be recorded in the eCRF.

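### The primary-endpoint rules score patients who stop ECP early in two ways, and the nonresponder rule has no Day 28 limit

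*Combined protocol and SAP*

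**What the plan says.** **Endpoint definition.** The synopsis (Study endpoints) and Sections 3.1, 3.2.1 and 9.3.1 define the primary endpoint as the proportion with CR or PR after four weeks (Day 28) of ECP. Each adds a clause for patients who had fewer treatments because they discontinued.

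**Nonresponder rule.** Section 9.3.1 also says that if a patient is given a second-line therapy other than ECP "or discontinues study treatment, that Patient will be considered a nonresponder". The synopsis (Statistical methods) and Section 6.6.1 apply the rule to anyone who has had any ECP: "or discontinues study treatment, that patient will be considered a nonresponder and may not be replaced". None of the three statements gives a time limit.

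**Treatment period.** Section 6.2.1 schedules ECP three times a week in Weeks 1-4 and twice a week in Weeks 5-12. Section 6.6.1 lists reasons for early cessation, one of which is "Condition no longer requires treatment".

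**Timing of the assessment.** The synopsis states: "The primary endpoint of overall response (CR+PR) at Day 28 (Week 4) will be summarized by frequency tabulation". Table 1 labels the Week 4 column "4 (Day 28) Primary Endpoint", and its footnote e says: "The assessment of aGvHD for the primary endpoint must occur at Day 28", with a window of two days either side. Section 7.2.2 agrees.

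**Data used.** Section 9.3.1 closes by restricting the formal analysis to data from a minimum of four weeks of ECP. Section 9.2 triggers the final analysis once all 48 patients have been treated for at least four weeks.

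**The concern.** There are two faults in the rule that fixes the numerator of the only confirmatory test.

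First, the endpoint definition can be read as assessing early stoppers for response on the treatment they received, while the nonresponder rule fails them whatever their status. Section 9.3.1 contains both. A programmer following one text and a programmer following the other could report different primary counts from the same data.

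Second, the nonresponder rule is broader than a Day 28 endpoint needs. Applied as written, a patient in CR or PR at Day 28 who leaves study ECP in Weeks 5-12, even because of improvement, is scored as a Day 28 failure. The same holds for a Day 28 responder who starts next-line therapy in those weeks.

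If neither is settled before the data are seen, the choice between readings in an open-label, single-arm trial could look driven by the results.

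**Working it through.** **1. The texts side by side**

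| Patient | Definition, read as assessing stoppers | Nonresponder rule as written | Rule limited to Day 28 |
|---|---|---|---|
| In PR, stops ECP in Week 3 | Responder possible | Nonresponder | Nonresponder |
| CR at Day 28, stops ECP in Week 7 | Responder | Nonresponder | Responder |
| PR at Day 28, next-line therapy in Week 9 | Responder | Nonresponder | Responder |

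The first row is the direct conflict. It disappears if the clause about fewer treatments means only that early stoppers stay in the denominator. Section 9.2 uses similar words when it sets the interim trigger, which suggests that meaning, but it is describing when to analyse and not how to score. The second and third rows show the missing time limit.

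**2. Inputs**

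From Sections 9.1, 9.2 and 9.3.1: n = 48, null rate p0 = 0.10, expected rate at least p1 = 0.27, exact binomial test, final two-sided threshold 0.049, stated power 90.4%. The documents give no rate of stopping or of next-line therapy in Weeks 5-12, so the share s of Day 28 responders reclassified is assumed to be 5%, 10% or 20%.

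**3. The stated power**

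Normal approximation: power = Φ[(p1 − p0 − z·SE0)/SE1].

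- SE0 = √(0.10 × 0.90/48) = 0.0433
- SE1 = √(0.27 × 0.73/48) = 0.0641
- z = 1.969 for two-sided 0.049
- (0.17 − 0.0852)/0.0641 = 1.323, so power is 90.7%

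This is close to the stated 90.4%.

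**4. Cut-off of the exact test**

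Against 10%, 9/48 gives P = 0.053 and 10/48 gives P = 0.025, so success needs at least 10 responders. One patient scored the other way can therefore change the outcome. Exact power at 27% is P(X ≥ 10) = 87.2%. This is lower than 90.4% because the exact test is discrete, which is a separate matter.

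**5. Effect of the literal rule**

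The counted rate becomes p(1 − s), and power is P(X ≥ 10) with X ~ Bin(48, p(1 − s)).

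| True Day 28 rate | s = 0 | s = 5% | s = 10% | s = 20% |
|---|---|---|---|---|
| 27% | 87.2% | 82.3% | 76.2% | 60.8% |
| 35% | 98.9% | 98.0% | 96.4% | 90.1% |
| 40% | 99.9% | 99.7% | 99.3% | 96.9% |
| 10% (false efficacy claim) | 1.9% | 1.3% | 0.9% | 0.4% |

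Allowing for an interim success at 8/24 (P = 0.0017) moves the 27%, 35% and 40% rows by at most 0.2 points.

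**6. Effect on the reported rate**

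From 13/48 (27.1%), reclassifying one, two or three responders gives 25.0%, 22.9% or 20.8%, all still significant. Reclassifying four gives 9/48 (18.8%), which fails.

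**The case against.** The strongest reply is that the broad reading is strained. The rule in 9.3.1 sits inside the definition of a Day 28 endpoint, and the synopsis, Table 1 and 7.2.2 all place the assessment there. Later outcomes have their own endpoints: response at Days 56 and 84, and duration through Week 16. In the synopsis and 6.6.1 the sentence belongs to a paragraph on replacing patients. The closing sentence of 9.3.1 includes the word *only*, which has little purpose unless it restricts the data. A final analysis triggered at four weeks also suits a Day 28 endpoint better than one left open to Week 12.

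Most of this stands as evidence of intent. It does not supply the rule. Fixing when status is measured does not say which later events may override it, and *at least* four weeks is a floor that Week 9 data also satisfy.

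The reply on size also has force. The shares are assumed, and 27% is the floor of the expected range. Section 1.1 cites overall response or improvement rates of 66% to 76% with ECP, though from small or retrospective series not measured at Day 28. At 66%, exact power is still 99.8% with 40% reclassified.

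Under the literal rule, early enrollees could be exposed to reclassification for up to 8 weeks longer than the last ones (12 − 4), but this is minor. With even accrual over 130 to 156 weeks (assumed from the 3-year duration in 10.9), 48 × 8/156 to 48 × 8/130 is about 2 to 3 patients.

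None of this removes the conflict over patients who stop before Day 28.

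**Conclusion.** The point holds as a conflict and an overbroad rule in the definition of the primary endpoint, of minor to moderate weight. The firmer part is the conflict over early stoppers, because the numerator depends on which text is followed. The missing Day 28 limit is real as written but probably unintended.

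The literal rule is conservative. It lowers the counted response rate and the power, with exact power at 27% falling from 87.2% to between 82.3% and 60.8% for assumed shares of 5% to 20%. The loss is small at rates well above 35%.

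A reader might infer three stronger things that the documents do not support:

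- **The sponsor will score post-Day 28 stoppers as failures.** The timing text points the other way.
- **The trial is underpowered.** The low figures need both the 27% floor and an assumed stopping share.
- **Type I error is inflated.** At a true 10% rate the chance of a false efficacy claim falls.

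Section 9.3 promises a separate formal SAP with full analysis details. The supplied text contains no such section, so the SAP may already settle both parts.

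**What to change.** State one analysis rule in the synopsis, 3.1, 3.2.1, 6.6.1 and 9.3.1:

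- The denominator is all patients with at least one ECP treatment.
- Next-line therapy or discontinuation of study ECP on or before the Day 28 (± 2 days) assessment, or no such assessment, counts as nonresponse.
- Events after that assessment do not change primary status.
- The clause about fewer treatments means that early stoppers stay in the denominator.

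Replace the closing sentence of 9.3.1 with an explicit Day 28 data cut. Add a sensitivity analysis that uses observed Day 28 status for patients who stopped earlier, including those who stopped because the condition no longer required treatment.

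The cost is wording and one extra table. Section 6.6.1 keeps patients who stop treatment in follow-up unless consent is withdrawn, so Day 28 status should often be available. Section 7.2.2, however, allows the weekly assessments to end at the visit when treatment stops, and should be reconciled with 6.6.1. Missing Day 28 assessments would count as nonresponse and should be reported. The change concerns scoring only and takes no view on when ECP should be stopped.
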